For an expansion cohort of approximately 35 subjects in the cervical, melanoma: prior anti-PD-(L)1, pancreatic, NSCLC: prior anti-PD-(L)1, and DLBCL cohorts, and an assumed true response rate of 30%, there is a 94% chance of observing at least 7 responses (in other words, the FNR is 6%). If the true response rate is only 10% rather than 30%, then there is a 6% chance that there will be at least 7 responses in 35 subjects (in other words, FPR is 6%). Also if 7 responses are observed (eg, 20% observed response rate), the lower bound of the 80% confidence interval (CI) for the ORR is 11% (higher than historical ORR of 10%). The CI is calculated using the Clopper-Pearson method.

For an expansion cohort of approximately 27 subjects in the bladder and SCCHN tumors and assumed true response rate of 50%, there is a 88% chance of observing at least 11 responses (in other words, the FNR is 12%). If the true response rate is only 25% rather than 50%, then there is a 5% chance that there will be at least 11 responses in 27 subjects (in other words, FPR is 5%). If 11 responses are observed (eg, 40% observed response rate), the lower limit of the 80% CI for the ORR is 28% (higher than historical ORR of 25%). The CI is calculated using the Clopper Pearson method.

For an expansion cohort of approximately 37 subjects with melanoma with prior anti-PD-(L)1 and anti-CTLA-4 therapy, and an assumed true response rate of 20%, there is a 85% chance of observing at least 5 responses (in other words, the FNR is 15%). If the true response rate is only 5% rather than 20%, then there is a 14% chance that there will be at least 5 responses in 37 subjects (in other words, FPR is 14%). Also, if 5 responses are observed (eg, 14% observed response rate), the lower bound of the 80% CI for the ORR is 7% (higher than historical ORR of 5%). The CI is calculated using the Clopper-Pearson method.

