The Simon 2-stage design will not be used for the mixed cohort of additional signal-seeking tumor types in Part 2. Approximately 35 to 40 subjects will be enrolled to allow for the exploration of early efficacy signals seen during the dose escalation portion of the trial as well as potential signals arising from ongoing trials of other IDO1 inhibitors in combination with anti-PD-(L)1. A 2-stage design will also not be utilized for the RCC and I-O naïve melanoma and NSCLC cohorts, as nivolumab is already an established standard of care in these settings. Approximately 40 subjects will be enrolled in each of these cohorts to allow for the exploration of early efficacy signals of BMS-986205 in combination with nivolumab.

Approximately 16 melanoma I-O naïve BRAF mutant subjects' post-BRAF inhibitor therapy will be randomized into 2 cohorts and will either be treated with nivolumab or nivolumab in combination with BMS-986205, but will not be used for formal statistical comparison.

Table 8.1.2-1: Dose Expansion: Example of Simon 2-stage Design Characteristics

Expansion Cohort	Historic ORR (%)	Target ORR (%)	Stage 1 /Total N	Stage 1 Responses Futility Boundary	Alpha/Power (%)	Probability of Early Stopping (%)
Cervical, Melanoma: Prior anti-PD-(L)1, Pancreatic NSCLC: Prior anti-PD-(L)1, and DLBCL	10	30	12/35	1	10/90	66
Bladder and SCCHN	25	50	10/27	2	10/90	53
Melanoma: Prior anti-PD-(L)1 and anti-CTLA-4	5	20	12/37	0	10/90	54

*Note: For the melanoma, prior anti-PD-(L)1, and prior anti-PD-(L)-1/anti-CTLA-4 cohorts, the analysis will be focused on approximately 35 subjects who are BRAF (wild-type) WT.

Abbreviations: CTLA-4 = cytotoxic T lymphocyte-associated antigen 4; DLBCL = diffuse large B cell lymphoma; I-O = immuno-oncology; NSCLC = non-small cell lung cancer; PD-1 = programmed cell death; PD-L1 = programmed death receptor-ligand 1; PD-(L)1 = either PD-1 or PD-L1; ORR = objective response rate; SCCHN = squamous cell carcinoma of the head and neck..

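### The false-positive rate given for at least 5 responses in 37 subjects at a true ORR of 5% is 14%; the exact value is 3.6% (3.2% with the stage 1 stop)

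*Combined protocol and SAP*

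**What the plan says.** Section 8.1.2 (Dose Expansion, Part 2) has three parallel paragraphs, one per cohort group. Each gives the chance of reaching a stated number of responses under the target and the historical ORR, followed by an 80% Clopper-Pearson lower bound. The synopsis (Statistical Considerations, Part 2) repeats them.

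The third paragraph opens "For an expansion cohort of approximately 37 subjects with melanoma with prior anti-PD-(L)1 and anti-CTLA-4 therapy". It makes three statements:

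- At a true ORR of 20%, "there is a 85% chance of observing at least 5 responses (in other words, the FNR is 15" per cent).
- "If the true response rate is only 5% rather than 20" per cent, "then there is a 14% chance that there will be at least 5 responses in 37 subjects (in other words, FPR is 14" per cent).
- If 5 responses are seen, "the lower bound of the 80% CI for the ORR is 7% (higher than historical ORR of 5" per cent).

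Table 8.1.2-1 (Table 3 in the synopsis) gives this cohort a stage 1/total N of 12/37, a stage 1 futility boundary of 0, alpha/power of 10/90 and a 54% probability of early stopping. A note to the table says that for the two pretreated melanoma cohorts "the analysis will be focused on approximately 35 subjects who are BRAF (wild-type) WT". The section describes the Simon design as guidance for cohort size and says that it is not a basis for hypothesis testing.

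**The concern.** A 14% chance of 5 or more responses in 37 is implausibly high when only 37 × 0.05 = 1.85 are expected. It also sits beside a lower confidence bound that excludes the historical rate, and the two statements cannot both be true.

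The paragraph tells the reader what 5 responses in this cohort would mean. As written, an inactive combination would reach that count about one time in seven, when the true figure is about one in 28. Five responses therefore look like weaker evidence than they are, and the cohort appears to have a higher false-positive rate than the 10% alpha in its own table row.

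**Working it through.** **Inputs.** From Section 8.1.2: N = 37, count ≥5, true ORR 5% (historical) and 20% (target). From Table 8.1.2-1: stop after stage 1 if 0 of 12 respond.

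**1. Calibrate on the neighbouring paragraphs.** Single-stage exact binomial tails, P(X ≥ r | n, p):

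| Cohort group | Rule | At target ORR | Stated | At historical ORR | Stated |
|---|---|---|---|---|---|
| Cervical and others | ≥7 of 35 | 93.5% (30%) | 94% | 5.5% (10%) | 6% |
| Bladder, SCCHN | ≥11 of 27 | 87.6% (50%) | 88% | 5.3% (25%) | 5% |

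Both paragraphs reproduce, so the document's method here is the single-stage binomial tail.

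**2. Same method, third paragraph, true ORR 5%.** For n = 37, P(X = 0, 1, 2, 3, 4) = 0.1499, 0.2919, 0.2765, 0.1698, 0.0760. These sum to 0.9641.

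P(X ≥ 5) = 1 − 0.9641 = **0.0359**, against 14% stated.

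**3. With the stage 1 stop.** Subtract the paths with 0 of 12 in stage 1 and ≥5 in the remaining 25:

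0.95^12 × P(≥5 of 25 | 5%) = 0.5404 × 0.00716 = 0.0039

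0.0359 − 0.0039 = **0.0321** (from unrounded values).

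The factor 0.5404 is the tabulated 54% early-stopping probability, so the table row and this calculation agree.

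**4. Does another reading give 14%?**

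- About 35 BRAF wild-type subjects, ≥5: 2.9% single-stage, 2.6% with the stop.
- ≥4 of 37: 11.2% single-stage, 9.3% with the stop.
- ≥3 of 37: 28.2% single-stage, 21.3% with the stop.
- Approximations for ≥5 of 37: Poisson 4.0%; normal 0.9% without and 2.3% with continuity correction.

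None gives 14%. A 14% tail for ≥5 of 37 needs a true ORR of about 7.5%.

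**5. Internal check.** The 80% Clopper-Pearson lower bound for 5 of 37 is the p at which P(X ≥ 5 | 37, p) = 0.10. That p is 0.0672, which rounds to the stated 7%. The tail rises with p, so at p = 0.05, below 0.0672, it must be under 0.10. The 7% bound is right, and it rules out 14%.

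**6. The paired 85%/15% at a true ORR of 20%.**

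- Single-stage: P(≥5 of 37) = 88.8%, FNR 11.2%.
- With the stop: 0.8880 − (0.8^12 × P(≥5 of 25 | 20%)) = 0.8880 − (0.0687 × 0.5793) = 0.8482, FNR 15.2%.

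The stated 85%/15% is therefore the two-stage value at N = 37. With their own stops, the two neighbouring paragraphs would read 87.5% and 85.1% instead of the stated 94% and 88%, so the three paragraphs do not share a basis.

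**7. Relation to the tabulated 10/90.** With the 0/12 stop, ≥4 of 37 gives 9.3% and 90.2%. That is the rule behind the table row. The text uses one response more.

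**The case against.** The best defence is about consequence. The two-stage design is guidance, the table is headed as an example, no hypothesis is formally tested, ORR is reported with a 95% interval, and a decision to end a cohort rests on all the efficacy data. Nothing makes 5 of 37 a go/no-go rule. The 14% did not produce N = 37, since the tabulated design is sound. The error also overstates false-positive risk, so it is conservative. All of this stands and limits the weight of the point. It does not make the figure right.

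Three stronger readings are tempting, and the documents support none of them.

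- A reader might infer that 85%/15% is also miscalculated, because it differs from the single-stage 88.8%/11.2%. It matches the two-stage value for the documented 12/37 design with boundary 0. What remains is an unlabelled change of basis.
- A reader might infer that the cohort misses its 10% alpha. The tabulated 10/90 belongs to ≥4 of 37 with the stop, not to the ≥5 in the text, and the true rate for ≥5 is well below 10% on either basis.
- A reader might put the discrepancy down to the BRAF wild-type note. The sentence itself says 37 subjects, and N = 35 gives 2.9%.

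**Conclusion.** The 14% false-positive rate is wrong as written in Section 8.1.2 and in the synopsis. The correct value is 3.6% single-stage or 3.2% with the stage 1 stop followed; the stated figure is 3.9 times the first (14/3.59) and 4.4 times the second (14/3.21). This rests only on the N, count, rate and stage 1 boundary that the documents give, with independent binary responses. The adjacent 7% bound confirms it from within the document.

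The 85%/15% stands as a two-stage figure whose basis needs stating. How the 14% arose cannot be established from the documents. This is a correction to a stated operating characteristic, worth making because the right value is certain, but of limited consequence.

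**What to change.** In the third paragraph on Part 2 sample size, in both Section 8.1.2 and the synopsis, replace the 14% and give both figures on one named basis:

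- **Single-stage**, matching the neighbouring paragraphs: FPR 4% (3.6%), power/FNR 89%/11% (88.8%/11.2%); or
- **Two-stage with the 0/12 stop followed**, labelled as such: FPR 3% (3.2%), power/FNR left at 85%/15%.

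The 80% lower bound of 7% stays. It would help to add that the tabulated 10/90 refers to ≥4 of 37 with the stop, whereas the text describes ≥5.

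The cost is a few numbers and a label in one paragraph, made in two places. Sample size, stage 1 rule and planned analyses are unchanged.

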- I-O naïve, BRAF mutated, post-BRAF-targeted therapy: Nivolumab is also approved for the treatment of first-line advanced melanoma across BRAF mutation status. Many of the BRAF mutated subjects who were treated in nivolumab trials had received prior BRAF-targeted therapy and still demonstrated clinical benefit with nivolumab. In addition, there is evidence of an increase in tumor infiltrating lymphocytes and an upregulation of PD-L1 following BRAF inhibition,²⁹ which suggests that the combination of an anti-PD-1 agent with an IDO1 inhibitor may be particularly beneficial in this subset of patients. However, there are not sufficient prospective data on the efficacy of nivolumab monotherapy (40 subjects per arm) in this population. Thus, these subjects will be randomized to receive either BMS-986205 in combination with nivolumab or nivolumab monotherapy in order to generate a robust, prospective dataset with nivolumab monotherapy to serve as a basis for understanding the potential added benefit of combination therapy.
- Prior anti-PD-(L)1 and prior anti-PD-(L)1 + anti-CTLA-4 combination regimen therapy: Recurrent or progressive melanoma following treatment with anti-PD-(L)1 monotherapy or the anti-PD-(L)1 + anti-CTLA-4 combination represents areas of high unmet medical need. These cohorts (approximately 35 subjects each) are added in order to assess whether IDO1 inhibition can act as a mechanism to restore anti-tumor activity in these subjects (refer to [Section 1.1.1](#) for supporting data).

NSCLC will also be evaluated in distinct settings:

- I-O naïve, PD-L1 positive and negative: Nivolumab is an approved therapy for the treatment of advanced NSCLC across PD-L1 status. These cohorts (40 subjects) are added in order to assess potential synergistic activity of adding IDO1 inhibition to a known standard of care.
- I-O experienced: Recurrent or progressive NSCLC following anti-PD-(L)1 therapy represents an area of high unmet medical need. This cohort (35 subjects) is added in order to assess if IDO1 inhibition can act as a mechanism to restore anti-tumor activity in these patients.

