3.1.6 Part 2: Dose Expansion

The purpose of dose expansion is to gather additional safety, tolerability, preliminary efficacy, PK, and pharmacodynamic information regarding BMS-986205 in combination with nivolumab.

Eight disease-restricted populations will be included in dose expansion. These include cervical cancer, DLBCL, SCCHN, bladder cancer, melanoma, NSCLC, RCC, and pancreatic cancer. Various subpopulations of melanoma and NSCLC will be included in separate cohorts to further

understand the role of IDO1 inhibition in these specific populations as described in [Section 1.1.5](#) and [Table 3.1.6-1](#)). An additional cohort will be dedicated to tumor types from the escalation inclusion criteria that do not currently have a dedicated expansion cohort or plans for evaluation in other studies. The eligible tumor types will be triple negative breast cancer, adenocarcinoma of the endometrium, epithelial cancer of the ovary, and sarcoma. Enrollment to this additional cohort will not exceed approximately 35 to 40 subjects. It will allow for the exploration of early efficacy signals seen during the dose escalation portion of the trial as well as potential signals arising from ongoing trials of other IDO1 inhibitors in combination with anti-PD-(L)1.

During dose expansion, the Simon 2-stage (optimal) design will be used as a guide for some of the tumor-specific expansion cohorts, although not used for hypothesis testing. Enrollment will continue for these tumor-specific expansion cohorts while evaluation of efficacy at stage 1 is ongoing. The 2-stage design with a reasonable false-positive rate (FPR) and false-negative rate (FNR) will provide guidance for the total sample size for these cohorts based on assumptions of true (target) and historic ORR for these indications. The sample sizes for each expansion cohort are provided in [Table 3.1.5-1](#).

Initially, guided by, a minimum of 10 subjects in the SCCHN and bladder tumor cohorts; 12 subjects in the cervical, pancreatic, DLBCL, melanoma with prior anti-PD-(L)1 therapy, and NSCLC with prior anti-PD-(L)1 therapy cohorts; and 12 subjects in the melanoma with prior anti-PD-(L)1 and anti-CTLA-4 therapy cohort will be treated in Stage 1 for an initial evaluation of efficacy.

Table 3.1.6-1: Part 2 Expansion Cohorts

Cohort	BMS-986205 + Nivolumab	Total Subjects (Approximately)
1	Cervical	35
2	DLBCL	35
3	SCCHN	27
4	Bladder	27
5	Pancreatic	35
6	Melanoma	
6a	Melanoma, I-O naïve, PD-L1 positive	40

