6b	Melanoma, I-O naïve, PD-L1 negative	40
6c*	BRAF-MT Melanoma, I-O naïve, post BRAFi	8
6d*	BRAF-MT Melanoma, I-O naïve, post BRAFi (nivolumab therapy)	8
6e	Melanoma, prior anti-PD-(L)1	35
6f	Melanoma, prior anti-PD-(L)1 and anti-CTLA-4	37
7	NSCLC	
7a	NSCLC, I-O naïve, PD-L1 positive	40
7b	NSCLC, I-O naïve, PD-L1 negative	40
7c	NSCLC, prior anti-PD-(L)1	35
8	Additional signal-seeking tumors	35
9	Renal cell carcinoma	40

NOTE: The BRAF-mutated, post-BRAF regimen melanoma subjects will be randomized to receive either nivolumab or BMS-986205 + nivolumab.

Abbreviations: BRAFi = BRAF inhibitor; CTLA-4 = cytotoxic T lymphocyte-associated antigen 4; DLBCL = diffuse large B-cell lymphoma; I-O = immuno-oncology; NSCLC = non-small cell lung cancer, PD-1 = programmed cell death-1; PD-L1 = programmed death receptor-ligand 1; PD-(L)1 = either PD-1 or PD-L1; SCCHN = squamous cell carcinoma of the head and neck.

Continuous evaluation of toxicity events in the dose expansions will be performed throughout enrollment in the expansion cohorts. If, at any time, the aggregate rate of treatment-related toxicities meeting DLT criteria exceeds 33% across all subjects treated in the dose expansions, the findings will be discussed and further enrollment may be interrupted. At that time, depending on the nature and grade of the toxicities and after assessing the risk/benefit ratio, a new dose(s) of BMS-986205 for all cohorts may be initiated at a previously tested lower dose level or at a dose level intermediate to previously tested lower dose levels. Additionally, at the discretion of the Sponsor, and in agreement with the investigators, the nivolumab 480 mg Q4W dosing

regimen in the designated expansion cohorts and clinical pharmacology substudy may revert back to 240 mg Q2W based on emerging PK, pharmacodynamic, and/or tolerability data from the cohort expansion portion of the study.

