iv) BRAF (V600) mutation status must be known. Both BRAF-mutated and WT subjects are permitted in this cohort.

**Note for the melanoma I-O naïve cohorts: If the PD-L1 status from the pre-treatment biopsy is not available prior to the start of treatment, subjects will be retrospectively assigned to the correct cohort once the result is available.

h) Melanoma: I-O Naïve, BRAF Mutated, Post-BRAF Inhibitor Therapy (Nivolumab with and without BMS-986205) [Numbers 6c and 6d in Table 3.1.6-1]

- i) Histologically confirmed, unresectable Stage III or Stage IV melanoma, as specified in the American Joint Committee on Cancer (AJCC) staging system. Subjects must have documented BRAF (V600) mutation and have had progressive or recurrent disease either during or after BRAF-targeted therapy in the unresectable or metastatic setting.
- ii) PD-L1 status must be documented if available. PD-L1 status will also be re-tested using tissue acquired from the mandatory pre-treatment biopsy.
- iii) Subjects must not have received prior systemic treatment in the unresectable or metastatic setting, except for BRAF- or BRAF/MEK-targeted therapy as stated above.

i) Melanoma, Prior Anti-PD-(L)1 Therapy (Number 6e in Table 3.1.6-1)

- i) Histologically confirmed, unresectable Stage III or Stage IV melanoma, as specified in the American Joint Committee on Cancer (AJCC) staging system.
- ii) PD-L1 status must be documented if available. PD-L1 status will also be re-tested using tissue acquired from the mandatory pre-treatment biopsy.
- iii) Must have had progressive or recurrent disease either during or within 6 months after anti-PD-(L)1 monotherapy. Subjects may have received other systemic therapies for their disease; however anti-PD-(L)1 targeted therapy must have been the most recent therapy administered.
- iv) BRAF (V600) mutation status must be known. Both BRAF-mutated and WT subjects are permitted in this cohort.

j) Melanoma, Prior Anti-PD-(L)1 and Anti-CTLA-4 Therapy (Number 6f in Table 3.1.6-1)

- i) Histologically confirmed, unresectable Stage III or Stage IV melanoma, as specified in the American Joint Committee on Cancer (AJCC) staging system.
- ii) PD-L1 status must be documented if available. PD-L1 status will also be re-tested using tissue acquired from the mandatory pre-treatment biopsy.

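### Cohorts 6e and 6f: the enrolment totals, the BRAF wild-type analysis note and the all-treated definition of ORR do not agree on who is analysed or how many

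*Combined protocol and SAP*

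**What the plan says.** Table 3.1.6-1 (Section 3.1.6) lists approximate total subjects of 35 for cohort 6e and 37 for cohort 6f ("Melanoma, prior anti-PD-(L)1 and anti-CTLA-4"). Neither row carries a BRAF qualifier. Section 1.1.5.1 also describes the two cohorts as totals: "These cohorts (approximately 35 subjects each) are added in order to assess whether IDO1 inhibition".

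Section 3.3.1 uses the same eligibility sentence for both cohorts: "Both BRAF-mutated and WT subjects are permitted in this cohort". It sets no limit on the number of mutated subjects.

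Section 8.1.2 computes its probabilities at the same sizes. For 6e the sentence opens "For an expansion cohort of approximately 35 subjects in the cervical, melanoma: prior anti-PD-(L)1, pancreatic" and continues that, at a true response rate of 30%, "there is a 94% chance of observing at least 7 responses". For 6f it opens "For an expansion cohort of approximately 37 subjects with melanoma with prior anti-PD-(L)1 and anti-CTLA-4 therapy" and gives 85% for at least 5 responses at a true rate of 20%, with a false positive rate of 14% at a true rate of 5%.

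The note under Table 8.1.2-1, repeated under Table 3 of the synopsis, then says of these two cohorts that "the analysis will be focused on approximately 35 subjects who are BRAF (wild-type) WT".

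Section 8.2 bases efficacy analyses on all treated subjects and lists no BRAF wild-type set. Section 8.3.1 defines ORR as a proportion of all treated subjects.

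**The concern.** A cohort of 35 that admits mutated subjects yields 35 wild-type subjects only if nobody mutated enrols. A cohort of 37 leaves room for two. The plan does not say whether 35 and 37 count wild-type subjects or everyone, whether the note's 35 is per cohort, or whether totals are raised to allow for mutated subjects. So either an enrolment figure or a probability is not delivered as stated.

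The denominator is also open. The table note points to wild-type subjects, and Sections 8.2 and 8.3.1 point to all treated subjects. ORR is one of the measures of the co-primary objective in Part 2. If the denominator is left unsettled until responses are known, it can be chosen after the fact, or appear to have been.

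**Working it through.** **Inputs.** From Section 8.1.2: n = 35, at least 7 responses, rates 10% and 30% (6e); n = 37, at least 5 responses, rates 5% and 20% (6f). From Table 8.1.2-1: 12 subjects in stage 1, stopping at 1 response or fewer (6e) or at 0 (6f). The documents do not give the share of BRAF-mutated subjects expected in these cohorts, so 10% to 50% is an assumption.

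**Formula.** Single-stage probability: P(X ≥ r | n, p) = 1 − Σ C(n,x) pˣ (1−p)ⁿ⁻ˣ, summed over x = 0 to r−1.

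**Step 1: reproduce the plan's figures.**
- 6e: P(X ≥ 7 | 35, 0.30) = 0.935 (stated 94%). P(X ≥ 7 | 35, 0.10) = 0.055 (stated 6%). Both reproduce.
- 6f: P(X ≥ 5 | 37, 0.20) = 0.888 (stated 85%). P(X ≥ 5 | 37, 0.05) = 0.036 (stated 14%). Neither reproduces.
- The 6f figure of 85% is matched by a two-stage calculation at n = 37 (0.848), or approximately by a single stage at n = 35 (0.857). The two-stage calculation gives 0.875 for 6e, so no single method at the stated sizes gives both 94% and 85%. The two-stage false positive rate for 6f is 0.032, so 14% is not explained that way either.

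**Step 2: room for mutated subjects.** 35 − 35 = 0 in 6e; 37 − 35 = 2 in 6f.

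**Step 3: 35 wild-type subjects analysed in each cohort.** 6e gives 0.935 and 6f gives 0.857, close to the stated 94% and 85%. The total to be enrolled is then 35/(1 − f), where f is the mutated share (last column below).

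**Step 4: 35 and 37 are totals, wild-type subjects are analysed, and the counts stay at 7 and 5.** Wild-type n is 35(1 − f) or 37(1 − f), rounded.

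| Assumed mutated share | 6e wild-type n | P(≥7 at 30%) | 6f wild-type n | P(≥5 at 20%) | Total per cohort for 35 wild-type |
|---|---|---|---|---|---|
| 10% | 32 | 0.887 | 33 | 0.818 | 39 |
| 20% | 28 | 0.780 | 30 | 0.745 | 44 |
| 30% | 24 | 0.611 | 26 | 0.617 | 50 |
| 40% | 21 | 0.449 | 22 | 0.457 | 59 |
| 50% | 18 | 0.278 | 18 | 0.284 | 70 |

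At 30%, 6e has 24.5 expected wild-type subjects; 25 instead of 24 gives 0.659.

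**Step 5: 35 wild-type subjects across both cohorts.** The note does not exclude this reading. Split as 17 and 18, it gives 0.225 (6e) and 0.284 (6f).

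**Step 6: what holding the counts fixed does.** In 6e at n = 24, the false positive rate for 7 responses at a 10% rate is 0.0075, against 0.055 at n = 35. Keeping 7 in a smaller set is therefore a stricter rule than the one described, and part of the loss in Step 4 comes from that.

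**The case against.** The strongest reply is that the note itself gives the size of the analysed set. At 35 wild-type subjects per cohort, 93.5% and 85.7% are close to what is stated. A reader might infer from the totals that 94% and 85% are simply wrong for the analysed set. The documents do not support that: on this reading the probabilities stand and the enrolment totals are what need changing. This part of the reply holds in full.

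Second, the sizes are approximate, and Section 8.1.2 calls the two-stage design a guide that is not used for hypothesis testing, with termination judged on the whole of the efficacy data. A reader might take 7 and 5 as binding decision rules and conclude that an active combination will be missed with the probabilities in Step 4. The plan contains no such rule, and nothing in it holds those counts fixed in a smaller set. This also stands. But approximate wording covers a subject or two, not a shortfall of 20% or 30%.

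Third, the note says the analysis is focused on wild-type subjects, not confined to them, and Sections 8.2 and 8.3.1 already use all treated subjects. That is a fair reading, but it restates the conflict: the note and those sections name different sets, and nothing says which governs.

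Finally, a reader might assume that 85% was computed at the full n = 37. A single-stage calculation at 37 gives 88.8%, so that cannot be taken for granted.

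**Conclusion.** The plan contradicts itself on the set and the number analysed in cohorts 6e and 6f. This rests on the text alone: totals of about 35 and 37, no cap on mutated subjects, a note pointing to about 35 wild-type subjects, and efficacy defined on all treated subjects.

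The consequence depends on which statement governs. If 35 wild-type subjects per cohort are analysed, the probabilities hold approximately and enrolment is understated: 39 to 70 per cohort would be needed at a mutated share of 10% to 50%. If 35 and 37 are totals and the wild-type set is the one judged, the stated probabilities do not hold for that set. They fall to between 0.89 and 0.28 in 6e and between 0.82 and 0.28 in 6f. Those ranges rest on an assumed mutated share and on unchanged guide counts, so they show sensitivity and are not a forecast. If all treated subjects are the denominator, the 6e figures stand.

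Separately, the 6f figures do not match their own n of 37 by the single-stage calculation that reproduces 6e.

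**What to change.** The simplest change adds no patients. Keep 35 and 37 as totals, apply the guide counts and ORR to all treated subjects as Section 8.2 already provides, and reword the note under Table 8.1.2-1 (and under Table 3 of the synopsis) so that BRAF wild-type is a named subgroup.

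If wild-type is meant to be the main set, define it in Section 8.2, say whether 35 is per cohort, state the mutated share assumed, and restate the guide counts and probabilities for the expected wild-type number. Under either choice, label the totals for 6e and 6f in Table 3.1.6-1 as all subjects or wild-type only.

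In the same edit, correct the 6f sentence in Section 8.1.2 and the synopsis. At n = 37, single-stage, the chance of at least 5 responses at 20% is 88.8% (false negative rate 100 − 88.8 = 11.2%), and the false positive rate at 5% is 3.6%. If a two-stage calculation was intended, say so and use it for every cohort.

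The cost is wording in two table notes, one table and one paragraph with its synopsis copy. The second option also means publishing less favourable probabilities or different counts. Whichever is chosen should be fixed before responses in these cohorts are analysed.
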